### **(c) Exploratory Outcome Measures:**

Measures of academic achievement, fluid cognition, and REREC are all considered exploratory.

C8. Analyses. For Hypothesis 1a, post-AT SDB as an outcome variable will be defined as a respiratory disturbance index (RDI)  $\geq 1$  obstructive or mixed apnea, hypopnea, or respiratory effort-related arousal per hour of sleep. The 22-item SDB scale score (on a continuous scale from 0.0 to 1.0^43) will provide the main explanatory variable. Logistic regression models will be assessed for sensitivity to potential covariates or confounds, including age, gender, race, body mass index z-score, and socioeconomic status. Secondary analyses will focus on RDI as a continuous outcome; validated snoring, sleepiness, and behavior subscales within the SDB scale; habitual snoring as a single, previously informative question-item; and most importantly SDB data generated by innovative algorithms, as described above, exploratory analyses for RCREC, esophageal pressures, and sleep dynamics. For Hypothesis 1b, multiple linear regression models will be constructed to assess cross-sectional associations between each neurobehavioral morbidity (the Behavioral Index being the primary outcome) and the SDB questionnaire score or RDI as the main explanatory variable. Models of the SDB questionnaire will use a slightly shortened, 16-item version (as previously) to exclude behavioral questions that would correlate with outcome measures for artificial reasons. Covariates as above will be taken into account. Secondary analyses will 1) assess the impact of SDB scores or RDI on other behavioral and cognitive measures; 2) take IQ and achievement into account within the main models; and 3) test the 3 newer, computed SDB measures in place of RDI. To assess Hypothesis 2a, the investigators will define adequate adherence as at least 4 hours of electronically recorded CPAP use per night, on average over the most recent 3 months on treatment. A series of multiple linear regression models will be used, with post-CPAP improvement in neurobehavioral variables as outcomes. The pre-CPAP SDB questionnaire scores or RDI will serve as the main explanatory variables. Secondary analyses will use the 3 SDB measures generated by computer algorithms as the explanatory variables. To assess Hypothesis 2b, the same outcomes will be regressed on CPAP adherent vs. non-adherent categorization, as well as (secondarily) a continuous measure of adherence as defined by mean hours of nightly use during the last 3 months of the trial. As with Hypotheses 1a and 1b, models for 2a and 2b also will be assessed after adjustment for similar potential covariates or confounds. To assess Hypothesis 2c, intent-to-treat analyses will use models that regress each primary neurobehavioral outcome on initial CPAP vs. control group assignment, after adjustment for BMI z-scores, age,

gender, race, and socioeconomic status. Exploratory models will in addition consider RDI (or computer algorithm proxy measures) and PSQ scores at 4 or 10 months post-AT, to assess whether residual SDB on these measures may explain differences in neurobehavioral outcomes. Exploratory analyses will also compare outcomes between CPAP-adherent subjects and controls, to assess (by contrast to the primary intent-to-treat analysis) what benefit may be lost by poor adherence, cross-overs, or drop outs.

In addition to standard SAS and Excel databases, REDCap (Research Electronic Data Capture) may be used for database development and data capture and management on this study as well as in tracking study activity. REDCap is a web-based electronic data capture system available under contract to the University of Michigan. Developed by Vanderbilt University, with collaboration from a consortium of institutional partners, REDCap provides a secure, web-based application designed to support data capture for research studies. REDCap is endorsed by the Michigan Institute for Clinical and Health Research (MICHR) and is part of larger data collection initiatives under the CTSA grant. REDCap was developed specifically around HIPAA-Security guidelines and has been disseminated for use locally at other institutions. By mid-2011, REDCap was being used by more than 200 academic/nonprofit consortium partners on six continents supporting more than 20,000 research end-users ([www.project-redcap.org](http://www.project-redcap.org)).

At the University of Michigan, the application is restricted to users on the UMHS Internal Network requiring a secure connection to communicate with U-M services i.e. VPN. The database is stored on a server separate from the application. Servers are maintained and supported by the Medical School Information Services (MSIS). REDCap Application support and services are provided by the Michigan Institute for Clinical and Health Research (MICHR).

**C9. Sample Size.** Plans are based on extensive preliminary data from the investigators on effects of AT for childhood SDB, and on the only quantitative preliminary data published, in 2009, for the neurobehavioral effects of CPAP in children with obstructive sleep apnea. Data from our group (section C9.3) show that the proportion of children, among those who undergo AT here for SDB, who have residual SDB 6 months later is about 50% or more, depending on criteria used to define SDB. Children with mildest SDB can have robust improvement in behavior, as measured with particular relevance for the current application on the Conners' ADHD Index. This improvement, by 0.5 standard deviations, is at least as strong as the that observed in more severe apneics. Yet, more than 0.5 standard deviations still separate Connors' scores in post-AT SDB patients from those in controls. The CPAP intervention we propose is a gold-standard widely believed to completely remedy any residual airway obstruction in adherent subjects. The CPAP may well, therefore, prove to be a more definitive treatment than AT in final elimination of even mild SDB. In a study of 21 children aged 6 to 16 years, with SDB of any severity and unselected for neurobehavioral problems, 3 months of CPAP was associated with robust improvement in inattention and hyperactivity on the Conners' scale ( $p<.001$  despite the limited sample) and in subjective sleepiness (Epworth,  $p<.001$ ). Adherence with PAP correlated with improvement in the Conners' measure ( $r=.48$ ,  $p=.03$ ) and the Epworth ( $r=.58$ ,  $p=.006$ ). These results emerged despite use of PAP by the subjects on only 56% of all nights on average. Our preliminary data (C9.7) suggest that we can expect about 67% our subjects to show adequate adherence.

Given these observations, we anticipate conservatively that a sample of 80 CPAP subjects who complete the protocol will contain about 40 with SDB ( $RDI>1$ ); that 53 will be adherent with PAP; and that most subjects with  $RDI>1$  along with some subjects who have  $RDI<1$  (but perhaps SDB symptoms) will benefit from PAP. For hypothesis 1a, to test for a correlation between SDB questionnaire scores and polysomnographically-defined SDB, we will have 80% power to detect a clinically meaningful Spearman correlation  $\rho \geq 0.25$  with  $\alpha=.05$ . Similarly, for hypothesis 1b, which focuses on an association between residual neurobehavioral problems and either SDB questionnaire scores or RDI, we will be able to detect a  $\rho \geq 0.25$ . For hypothesis 2a, with about 27 post-AT, CPAP-adherent subjects who have  $RDI>1$  and 26 who have  $RDI<1$ , we will have 82% power to reject the null hypothesis (that the mean 6-month change scores in the Behavioral Index for the two groups are equal) if the effect size is  $\geq 0.8$ . The likelihood of this result is based on observations in our previous studies with the Conners' ADHD Index, which is a main component of the Behavioral Index now proposed. Based on improvement we have measured in the past after AT for children with mildest levels of SDB, for the current hypothesis 2b, in which we will compare about 53 treated (adherent) to 27 non-treated (non-adherent) residual apneics, we should have power of 0.78 to detect an effect size  $\geq 0.65$ . This effect size is substantially smaller than that implied by the correlations above among 21 children and by our own preliminary data below. For

*hypothesis 2c, comparison of 80 CPAP-treated subjects to 40 controls should provide 80% power to detect a Behavioral Index difference between groups (effect size)  $\geq 0.55$ . The 120 subjects will be recruited from the 2,475 children aged 5-12 years anticipated to have AT at the two otolaryngology practices during 3 years and 4 months of study enrollment. In each of two previous R01 studies here that followed children for 12 or 6 months after AT, attrition was only 5% with careful attention to each family from an experienced project manager. The study now proposed will conservatively anticipate 10% attrition, and target enrollment of 132 subjects.*

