The investigators therefore propose a highly practical, clinical study with **two main goals: (1) to assess the extent that behavior, cognition, and sleepiness in children can improve with CPAP after AT, and (2) to identify which patients stand to gain most from post-operative assessment and treatment.** This research will use reversible SDB-related neurobehavioral morbidity as the criteria by which to judge the utility of clinical symptoms and polysomnography in identification of candidates for CPAP after AT. Neurobehavioral outcomes will be assessed with instruments shown to be sensitive to SDB in the past. Clinical sleep symptoms will be assessed by use of a pediatric SDB questionnaire developed and validated by the investigators and now used around the world. Standard polysomnography will be supplemented by innovative approaches shown by the investigators to help identify subtle pediatric SDB. Subjects will be 5-12 years old and have had AT in recent months for suspected SDB. To enroll a reasonable distribution of children with and without obvious SDB symptoms after AT, the sample will be enriched selectively if necessary. *All analyses will be adjusted for body mass index z-scores.* These novel investigations will come at a critical juncture and could well transform clinical care for an exceedingly common and consequential childhood condition.

**Aim 1:** Complete parental sleep questionnaires, sleep laboratory-based nocturnal polysomnograms, Multiple Sleep Latency Tests of daytime sleepiness, parental behavioral ratings, and neuropsychological tests for  $n=120$  children 4 months after AT for clinically suspected or laboratory-confirmed SDB.

**H1a:** After AT, an SDB symptom scale will help identify children who have residual SDB on polysomnography.

**H1b:** After AT, residual problems with behavior, cognition, and sleepiness will show associations with persistent SDB as identified by the SDB scale or polysomnography.

**Impact:** Results will show that after AT, a symptom-based questionnaire can help identify children likely to have residual SDB, which in turn is a risk factor for persistent neurobehavioral morbidity. Clinicians and families will have, for the first time, data that can guide evaluation after an exceedingly common surgery.

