**C10.2.** The pediatric SDB questionnaire to be used in this study was developed and validated by the investigators, and shown to be useful in many research studies. The 22-item SDB component of the Pediatric Sleep Questionnaire asks about chronic snoring, snorting, observed apneas, other breathing difficulties, ancillary symptoms, and behavioral signs (see appendix), each of which individually predicts childhood SDB as confirmed by polysomnography. The scale can be licensed online from the University of Michigan by any investigator at no cost. When tested against polysomnographically-defined pediatric SDB, the SDB scale showed a sensitivity of 0.81, specificity of 0.87, and overall classification accuracy of 85%, with good internal consistency and test-retest reliability. In a subsequent study of 78 children who underwent AT for clinical purposes, and 27 controls, the SDB scale identified subjects with polysomnographically-confirmed SDB both before and one year after AT. The SDB scale predicted current hyperactive behavior, sleepiness (mean sleep latency), and their responses to AT at least as well as sleep studies did. However, these important findings require confirmation, as the original aims of the research did not include these analyses. Furthermore, no data were collected on response to PAP. Nonetheless, the SDB scale is now used in many studies at the University of Michigan, elsewhere in the U.S., and around the world, where it has been translated (at minimum) into Spanish, German, Chinese, and Turkish, with Korean and Portuguese versions in progress.

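### H1a is about helping to identify children with residual SDB, but it is analysed and sized only as an association; a significant result alone would not show that the scale identifies them usefully

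*Combined protocol and SAP*

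**What the plan says.** Section 2.2, Aim 1, states H1a as: "After AT, an SDB symptom scale will help identify children who have residual SDB on polysomnography". The impact statement says results will show that "a symptom-based questionnaire can help identify children likely to have residual SDB" and will give clinicians and families data to guide evaluation after surgery.

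Section C8 defines the H1a outcome as RDI >= 1. The continuous 22-item score "will provide the main explanatory variable", with no cut-off on the score. It adds: "Logistic regression models will be assessed for sensitivity to potential covariates or confounds". In that sentence, sensitivity means robustness to covariate adjustment, not diagnostic sensitivity. The secondary H1a analyses (continuous RDI, subscales, a single snoring item, algorithm-based measures) are again associations.

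Section C9 gives the sizing: "we will have 80% power to detect a clinically meaningful Spearman correlation" of at least 0.25 at alpha 0.05. Aim 1 has 120 children.

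Two other places matter. Section C10.2 reports that in earlier work "the SDB scale showed a sensitivity of 0.81, specificity of 0.87". Section C2 treats a score above 0.33 as positive, for the enrichment rule. Neither is tied to an accuracy estimate for H1a. Section C1 says standard cut-offs will be applied first to test H1a, but it also names no accuracy measure.

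**The concern.** Helping to identify affected children is a question about classification: given the score, how often is the child's SDB status called correctly? An odds ratio or correlation tests whether the score and SDB status are related at all. With 120 children, a scale that sorts them well and one that sorts them poorly can both give p<0.05, and the planned analysis does not separate the two.

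This matters because the stated use is practical. Section A7 expects the study to inform the role of the questionnaire and the indications for post-operative polysomnography. Section A3 warns that surgery may reduce or hide symptoms while SDB persists. That failure would appear as false negatives, which a p-value for the score does not reveal.

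**Working it through.** **Inputs.** n = 120 (Aim 1); rho = 0.25, alpha 0.05, power 80% (C9; two-sided assumed, as the sides are not stated). Prevalence of residual SDB: about 50% or more (C9); 66% with RDI > 1 and 47% with RDI >= 1.5 in the earlier cohort of 135 (C10.3). That cohort was studied at 6 months, so its figures are only a guide to RDI >= 1 at 4 months.

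**Step 1: the plan's own figure.** Fisher z: power = Phi(atanh(0.25) x sqrt(117) - 1.96) = Phi(0.2554 x 10.817 - 1.96) = Phi(0.803) = 78.9%. Variance factors specific to Spearman give 76.5% to 77.7%. Simulation with a binary outcome gives about 77% to 78% for Spearman and about 80% for a t-test. The stated 80% is reproduced closely enough, so power is not the problem. The smallest correlation that reaches significance is tanh(1.96/sqrt(117)) = 0.179.

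**Step 2: what a correlation implies for classification.** Assume normal scores with equal variance in the two groups, and prevalence p.

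- Standardised difference: d = r / sqrt(p(1-p)(1-r^2)). At r = 0.25, p = 0.5: 0.25 / sqrt(0.25 x 0.9375) = 0.516.
- AUC = Phi(d/sqrt 2) = Phi(0.365) = 0.642.
- At the equal-error cut-off, sensitivity = specificity = Phi(d/2) = Phi(0.258) = 0.602, so 39.8% are misclassified.
- At p = 0.66: d = 0.545, AUC 0.650, sensitivity = specificity = 0.607.
- PPV = 0.66 x 0.607 / (0.66 x 0.607 + 0.34 x 0.393) = 0.75.
- NPV = 0.34 x 0.607 / (0.34 x 0.607 + 0.66 x 0.393) = 0.44.

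| rho | prevalence | AUC | sens = spec | misclassified | PPV | NPV |
|---|---|---|---|---|---|---|
| 0.18 | 50% | 0.60 | 0.57 | 42.7% | 0.57 | 0.57 |
| 0.18 | 66% | 0.61 | 0.58 | 42.3% | 0.73 | 0.41 |
| 0.25 | 50% | 0.64 | 0.60 | 39.8% | 0.60 | 0.60 |
| 0.25 | 66% | 0.65 | 0.61 | 39.3% | 0.75 | 0.44 |
| 0.50 | 50% | 0.79 | 0.72 | 28.2% | 0.72 | 0.72 |
| 0.50 | 66% | 0.81 | 0.73 | 27.1% | 0.84 | 0.58 |

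**Step 3: dependence on the assumptions, at rho 0.25.** The rank relation AUC = 0.5 + rho / (2 sqrt(3p(1-p))) gives 0.644 at 50% and 0.652 at 66%, with 39.7% and 39.1% misclassified. A median split of a latent bivariate normal gives 42.0%. The accuracy-maximising cut-off at 66% prevalence gives 32.6%, against 34% if every child is simply called positive.

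**Step 4: precision of accuracy estimates with 120 children.**

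- AUC 0.64 with 60 v 60: Hanley-McNeil SE 0.050, half-width about 0.10.
- Sensitivity 0.81, n = 60: 1.96 x sqrt(0.81 x 0.19/60) = 0.10.
- Sensitivity 0.60, n = 60: 0.12.
- Specificity 0.607 at 66% prevalence, n about 41 (0.34 x 120): 0.15.
- NPV 0.44, n about 56 score-negative children: 0.13.

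**The case against.** The strongest reply is that H1a promises only help in identification, and an association gives that some support. At rho 0.25 and 66% prevalence, SDB would be present in 75% of score-positive and 56% of score-negative children (1 - 0.44). This stands. A reader might infer that a positive H1a result cannot support the stated claim at all. The documents do not bear that out, because the claim is worded modestly.

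A reader might also infer that about 40% of children will be misclassified. That does not follow either. The 0.25 is the smallest effect with 80% power, not the expected effect. The 40% also needs a distributional model and a cut-off that the plan does not specify.

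The earlier 0.81 and 0.87 are tempting as a pass mark. Section C10.2 does not give the population or score cut-off behind them, and section A6 cautions, about polysomnographic thresholds, that what works before surgery may not suit the setting after it.

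On weight: H1a is not among the primary or secondary outcomes in C7, section 6.5 calls the trial early-stage, and testing association is common at that stage. A logistic model also yields predicted probabilities, from which accuracy could be computed. All of this limits the seriousness of the point. It does not supply the missing estimate or fix the cut-off in advance.

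**Conclusion.** The point holds as a mismatch between hypothesis and analysis. A significant association alone does not establish useful identification: it can arise with an AUC near 0.60 (about 43% misclassified, at the significance threshold) or near 0.80 (about 28%, at rho 0.5), and the plan commits to nothing that tells these apart. At the effect the plan calls clinically meaningful, discrimination is weak. The error figures assume a binormal score and, for the headline values, an equal-error cut-off; the predictive values also assume the stated prevalence.

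The power statement is sound and the primary outcome (H2c) is not affected. The change is worth making because H1a's conclusion is aimed directly at practice.

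**What to change.** In C8, make the lead H1a estimate the AUC of the 22-item score for RDI >= 1 with a 95% CI. Add sensitivity, specificity, PPV and NPV with 95% CIs at the >0.33 score already stated in C2. Fixing that cut-off in advance matters because one chosen after seeing the data would overstate accuracy. Word the H1a conclusion from these estimates and keep the logistic model as support. Cite the earlier 0.81 and 0.87 only as descriptive context.

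In C9, state the expected precision: about +/-0.10 for the AUC and about +/-0.10 to 0.15 for sensitivity, specificity and predictive values.

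If the enrichment rule was used, say that all the accuracy measures may be affected, predictive values included, because C2 selects on both the pre-operative and the 4-month score. Show results separately for children enrolled with and without the score requirement.

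The cost is SAP wording plus one ROC analysis and a 2x2 table from data already planned. The downside for the investigators is that a significant but weak association could no longer be presented as evidence that the scale usefully identifies residual SDB.

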**Aim 2:** *Randomize Aim 1 subjects to receive 6 months of standard clinical care (control group,  $n=40$ ) vs. CPAP titration (CPAP group,  $n=80$ ), home use of CPAP, and monitored adherence; and then re-assess all subjects with all baseline sleep and neurobehavioral tests.*

**H2a:** Among CPAP subjects who have adhered to the therapy, residual questionnaire or polysomnographic evidence of SDB from 4 months post-AT, as compared to no residual SDB, will predict greater improvement 10 months post-AT in hyperactive behavior, attention deficit, and sleepiness.

**H2b:** Among all CPAP subjects ( $n=80$ ), neurobehavioral outcomes will improve more, from baseline to follow-up, among subjects who adhere successfully to CPAP than among those who do not.

**H2c:** *Among all subjects ( $n=120$ ), neurobehavioral outcomes will improve more among CPAP subjects than control subjects in an intent-to-treat analysis.*

**Impact:** Results will demonstrate the clinical utility of an SDB questionnaire and polysomnography after AT; implicate post-AT residual SDB as a potential cause of persistent neurobehavioral problems; and suggest that successful treatment of post-AT SDB provides tangible clinical benefits.

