Approximately ten months after AT (six months after randomization), sleep studies (on steady PAP for the CPAP subjects, without PAP for controls) and neurobehavioral assessments will all be repeated. The sleep study is required to precede a valid Multiple Sleep Latency Test; will allow confirmation in CPAP subjects that any SDB is well controlled; and will allow reassessment for residual SDB in the control group. The 6-month interval is selected to ensure adequate time for PAP habituation, neurobehavioral response to consistent use of PAP, and acceptably low risk of test-retest learning effects on cognitive measures. The outcome measures have been used by the investigators in two NIH-funded R01s (HD038461 and HL080941) over the past 10 years and all derive from well-validated, widely accepted instruments. The explanatory polysomnographic measures are all consistent with American Academy of Sleep Medicine 2007 standards. Esophageal pressure monitoring, with which this laboratory has extensive clinical, research, and published experience, will be used to provide a gold-standard assessment of respiratory effort. In addition, at least 3 highly innovative, most promising, and particularly sensitive computerized measures, all pioneered previously in children by the investigators, will be available to complement standard analyses. These include respiratory cycle-related EEG changes (RCREC) thought to reflect subtle but numerous and consequential inspiratory microarousals; an analysis of sleep dynamics, which focus on continuity of sleep and specific sleep stage bouts rather than traditional totals of time spent in each stage; and quantitative analysis of esophageal pressure swings during each respiratory cycle through the night. Based on the investigators' preliminary data (see below and section C9.5), these automated measures may well improve the ability of pediatric polysomnography to distinguish children with and without clinically significant SDB and potential to benefit from CPAP.

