Change in **NIH Toolbox Total Composite Score Age Adjusted** from SV2 to SV4 in CPAP adherent subjects

will be associated with SRBD score at SV2

12. Among adherent CPAP users residual SRDB score at SV2 will predict greater improvement at SV4 for subjective sleepiness (hypothesis 2a)

Change in **ESS** from SV2 to SV4 in CPAP adherent subjects will be associated with SRBD score at SV2

13. Among adherent CPAP users residual SRDB score at SV2 will predict greater improvement at SV4 for objective sleepiness (hypothesis 2a)

Change in **MSLT** from SV2 to SV4 in CPAP adherent subjects will be associated with SRBD score at SV2

14. Among adherent CPAP users residual SRDB score at SV2 will predict greater improvement at SV4 for quality of life (hypothesis 2a)

Change in **PedsQL** from SV2 to SV4 in CPAP adherent subjects will be associated with SRBD score at SV2

15. Among adherent CPAP users AHI at SV2 will predict greater improvement at SV4 for behavior (hypothesis 2a)

Change in **behavioral index** from SV2 to SV4 in CPAP adherent subjects will be associated with AHI at SV2

16. Among adherent CPAP users AHI at SV2 will predict greater improvement at SV4 for cognition (hypothesis 2a)

Change in **NIH Toolbox Total Composite Score Age Adjusted** from SV2 to SV4 in CPAP adherent subjects will be associated with AHI at SV2

17. Among adherent CPAP users AHI at SV2 will predict greater improvement at SV4 for subjective sleepiness (hypothesis 2a)

Change in **ESS** from SV2 to SV4 in CPAP adherent subjects will be associated with AHI at SV2

18. Among adherent CPAP users AHI at SV2 will predict greater improvement at SV4 for sleepiness (hypothesis 2a)

Change in **MSLT** from SV2 to SV4 in CPAP adherent subjects will be associated with AHI at SV2

19. Among adherent CPAP users AHI at SV2 will predict greater improvement at SV4 for quality of life (hypothesis 2a)

Change in **PedsQL** from SV2 to SV4 in CPAP adherent subjects will be associated with AHI at SV2

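### Hypothesis 2a is tested only in adherent CPAP children, so it cannot show which children benefit from CPAP; no arm-by-SDB interaction is planned

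*Combined protocol and SAP*

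**What the plan says.** Section 2.2 gives the second main goal as "to identify which patients stand to gain most from post-operative assessment and treatment". H2a in the same section is the hypothesis meant to answer the treatment part of it. It is confined to one subgroup of one arm: "Among CPAP subjects who have adhered to the therapy, residual questionnaire or polysomnographic evidence of SDB from 4 months post-AT" is to predict greater improvement 10 months after AT.

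C7(b) turns this into ten of the 19 secondary outcomes. Items 10–14 use the SRBD questionnaire score at SV2 and items 15–19 use AHI at SV2, for example "Among adherent CPAP users AHI at SV2 will predict greater improvement at SV4 for behavior". In every item the outcome is SV2-to-SV4 change among adherent CPAP children.

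C8 gives the model: "A series of multiple linear regression models will be used, with post-CPAP improvement in neurobehavioral variables as outcomes". The main explanatory variables are the pre-CPAP questionnaire score or RDI. Covariates are to be similar to those for H1a and H1b (age, gender, race, BMI z-score, socioeconomic status). The outcome's own SV2 value is not listed.

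C9 powers H2a as 27 adherent children with RDI above 1 against 26 below 1: "we will have 82% power to reject the null hypothesis" at an effect size of 0.8.

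Controls are assessed at the same times. C3 has the 10-month sleep studies done "without PAP for controls) and neurobehavioral assessments will all be repeated". For H2c, C8 adds: "Exploratory models will in addition consider RDI" (or proxy measures) and questionnaire scores at 4 or 10 months, to see whether residual SDB explains outcome differences. No interaction with arm is named there or elsewhere.

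**The concern.** A child's change over six months is what would have happened without CPAP plus any effect of CPAP. A slope of change on SDB inside a treated group estimates the sum of two slopes: SDB with change in any child, and SDB with gain from CPAP. Goal 2 needs the second alone, and only a comparison with untreated children isolates it.

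The first slope need not be zero. C10.2 reports, from a study with no PAP data: "The SDB scale predicted current hyperactive behavior, sleepiness (mean sleep latency), and their responses to AT". C3 has a parent complete both the behaviour scales and the sleep questionnaire during the child's testing, so transient rating error can be shared between predictor and baseline outcome. Regression to the mean then produces an SDB–change slope with no CPAP effect.

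The restriction to adherent children adds selection after randomisation, with no identifiable counterpart among controls.

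At stake is how a positive H2a result may be read. It would be presented as evidence for selecting CPAP candidates after AT, but it could not support the statement that these children benefit from CPAP.

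**Working it through.** **1. The plan's figure.** Inputs from C9: 27 vs 26 children, difference 0.8 SD of change; two-sided 5% is assumed. SE = √(1/27 + 1/26) = 0.275. Normal power = Φ(0.8/0.275 − 1.96) = 82.9%; noncentral t gives 81.5%. The stated 82% is reproduced.

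**2. What that power refers to.** It is the chance of finding an SDB–change association in one treated group. If children with SDB changed 0.8 SD more in both arms, so that CPAP benefit had nothing to do with SDB, H2a would reject equally often, about 82%. A shared difference of 0.5 or 0.3 SD would give 43% or 19%. A valid interaction test would reject 5% each time.

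**3. False positives with zero CPAP effect.** S is SDB at SV2, B2 and B4 are behaviour at SV2 and SV4, ρ is the S–B2 correlation, r is the B2–B4 correlation. All correlations are assumptions: ρ = 0.1, 0.25, 0.4 and r = 0.5, 0.7.

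- Null A: S relates to B4 only through the observed B2. Then corr(S, change) = ρ(1−r)/√(2(1−r)). For ρ = 0.25 and r = 0.5 this is 0.125.
- Null B: S relates to a stable trait that enters B2 and B4 equally, so corr(S, change) = 0.

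Rejection rates in 20,000 replicates (ranges cover r = 0.5 and 0.7):

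| Model | Null | ρ = 0.1 | ρ = 0.25 | ρ = 0.4 |
|---|---|---|---|---|
| Planned change model, n = 53 | A | 5.9–6.2% | 10.9–14.4% | 19.7–29.9% |
| Planned change model, n = 53 | B | about 5% | about 5% | about 5% |
| Single arm plus SV2 value, n = 53 | A | about 5% | about 5% | about 5% |
| Single arm plus SV2 value, n = 53 | B | 6.4–6.7% | 12.1–18.2% | 26.5–44.4% |
| Arm × SDB plus SV2 value, 80/40 | A and B | 4.9–5.2% | 4.9–5.2% | 4.9–5.2% |

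Each single-arm model is safe under one null and not the other, and nothing in the plan shows which applies. The interaction holds its level under both.

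**4. Precision of the interaction.** Take 80 CPAP and 40 control children, half with SDB. C9 gives about 40 of 80 in the CPAP arm; the same share is assumed in controls.

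- SE = √(1/40 + 1/40 + 1/20 + 1/20) = 0.387 SD of change.
- Power at 0.8 SD: 54%. Detectable with 80% power: about 1.09 SD.
- 95% CI half-width: 1.98 × 0.387 = 0.77 SD.
- Completers for 80% power at 0.8 SD, 2:1 allocation: 18 × ((1.96 + 0.84)/0.8)² ≈ 221, against 120 planned.
- Adjusting for the SV2 value raises the 54% to about 60% (r = 0.7) or 66% (r = 0.5).
- If non-adherent children gain nothing (53 of 80 adherent), 0.8 SD among adherent children becomes 0.8 × 53/80 = 0.53 SD by assignment, with about 27% power. Conversely, 1.09 SD by assignment needs 1.09/(53/80) = 1.65 SD among adherent children.

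**The case against.** **The evidence for a prognostic link is indirect.** AT is itself a treatment for SDB, so a scale that predicted response to AT may have been picking up a true difference in treatment effect. C10.2 says those findings need confirmation. This is right: the passage makes a link possible and does not establish it.

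**Natural recovery is limited by design.** C3 places SV2 at four months because most behavioural gain after AT comes in the first three. That narrows one route but leaves regression to the mean and shared rating error.

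**The inflation may be small or absent.** It is nil under Null B and about 6% at a correlation of 0.1. Sections A3 and A6 report no consistent linear relation of polysomnographic measures with behaviour, which weakens the point for items 15–19. With the two-group split that C9 powers, approximated as a median split, the Null A rates fall to 8–11% at 0.25 and 14–21% at 0.4. All this stands and limits the size of the problem, but it does not give the single-arm slope a who-benefits meaning.

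**The remedy asks a different question with low power.** A4 explains the adherent focus: only adherent PAP use can be assumed to resolve SDB almost completely. The interaction concerns assignment, with about a third non-adherent. That is a real cost. It argues for an estimate with an interval and a modest claim, not for reading a within-arm association as benefit.

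**The exploratory models may cover it.** Their form is left open, but no interaction is named. The 10-month values are post-randomisation, with CPAP children studied on PAP. The adherent-versus-control comparison addresses benefit lost through poor adherence.

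**Conclusion.** The concern holds. H2a, C7(b) items 10–19, C8 and C9 all estimate an association within adherent CPAP children, whereas goal 2 asks who gains from CPAP. The missing interaction is a matter of record, and the data to estimate it are collected.

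The size is conditional. With no CPAP effect, the planned test's error rate runs from its nominal 5% up to 20–30%, depending on assumed correlations and on how SDB relates to behaviour over time. The concern is greater for the parent questionnaire (items 10–14) than for AHI or RDI (items 15–19). A spurious finding is possible, not certain.

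This should be fixed, but it is limited in reach: H2a is secondary, section 6.5 describes the trial as early stage, and the primary intent-to-treat comparison is not touched.

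**What to change.** - Specify in C8 a treatment-arm by SV2-SDB interaction in all randomised children, with the outcome's own SV2 value as a covariate. Make it the analysis behind any statement about who benefits, and report the estimate with its 95% CI.
- Present the adherent-CPAP slope beside the control slope as descriptive. If the interaction is not adopted, label H2a and C7(b) items 10–19 as prognostic associations.
- Do not add the SV2 outcome value to the single-arm model as a stand-alone remedy; that moves the inflation from Null A to Null B.
- State in C9 that the 82% applies to the within-CPAP contrast only.

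The change is to analysis wording and needs no new data. The cost is a more modest claim, because with 120 completers the interaction will be estimated with a wide interval.
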